## **Description of Subject Population**

#### Sample #1

Specify subject population Adults with CUD Number of completers required to accomplish study aims 60 Projected number of subjects who will be enrolled to obtain required number of completers 80 Age range of subject population 18-65

Gender, Racial and Ethnic Breakdown

Based on on-going research, it is expected that 20-30% of applicants will be female and 30% will have an ethnic identity of Hispanic. In terms of race, 30-40% are estimated to be Caucasian, 60-70% African American, and 5% Native American, Asian and Pacific Islanders, Eskimos, or Aleuts. Description of subject population

Description of subject population

We plan to enroll 80 participants into the study who meet criteria for current CUD and all other study criteria.

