## **Study Procedures**

Describe the procedures required for this study

*Study Participants*: Participants will be 80 men and nonpregnant women with CUD who report using cannabis a minimum of 5 days per week over the past 28 days. The minimum threshold of a near-daily pattern of cannabis use will select a population with moderate-to-severe CUD. This level of severity is consistent with the sample in our previous clinical trial (Levin et al. 2011), and, we suspect, typical of individuals with CUD who seek treatment. This sample is less likely to achieve abstinence spontaneously or in response to non-medication aspects of the trial (e.g., general therapeutic support), and thereby minimize the placebo response rate. Selecting for near-daily cannabis users will also prevent a "floor effect" (i.e., participants using cannabis infrequently at baseline would be unlikely to demonstrate significant improvement).

**Inpatient phase**: Patients seeking cannabis treatment will move into the inpatient unit at NYSPI for 5 nights. On move-in day, participants will only receive the PM capsule administration; all capsules will be given under observation and will be double blind. During the next 4 days (days 2-5; Table 1), we will measure medication effects on cannabis withdrawal, including measures of mood, cannabis craving,

objective and subjective measures of sleep, and food intake in our Outpatient Marijuana Laboratory. Cannabis relapse measures will begin following discharge on day 6.

**Outpatient phase**: After discharge from the inpatient phase, 12-weeks of outpatient treatment will be conducted (Table 2). Study visits will occur twice weekly. One visit per week will be with the research psychiatrist for a Medical Management session to perform study assessments and to monitor medication effects and compliance. Participants will have a manual-guided (Pettinati et al. 2005) supportive behavioral treatment session with the research psychiatrist each week. This psychosocial intervention facilitates compliance with study medication and other study procedures, promotes abstinence from cannabis and other substances, and encourages mutual-support group attendance. The second visit each week will be for vital sign monitoring, urine toxicology and completion of self-report measures. Participants will be given cash incentives contingent on study visit attendance and completing other study procedures with the objective of achieving a high treatment adherence.

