#### **Outpatient Study Assessments**

Adverse Effects measures: The Systematic Assessment for Treatment and Emergent Events (SAFTEE; Johnson et al. 2005) adapted for clonazepam will be performed weekly to identify adverse symptoms. Benzodiazepine withdrawal measure: The Clinical Institute Withdrawal Assessment-Benzodiazepines (CIWA-B)(Busto, 1989) is a 22-item scale to assess the degree of benzodiazepine withdrawal. Cannabis Craving measure: The Marijuana Craving Questionnaire (MCQ) is a 47-item instrument (Heishman et al. 2001).

Columbia Suicide Severity Rating Scale: Will be used to monitor suicidality at baseline and twice a month during the study period.

Medical Evaluation and Monitoring: A medical history and physical exam will be performed during screening. Serum pregnancy testing will be performed during screening and urine pregnancy testing will be performed monthly during the study. Complete blood count, electrolyte, urinalysis and liver function tests will be performed during screening and monthly during the study. Height and weight will be measured and baseline body mass index (BMI) calculated during screening. Temperature, pulse, blood pressure, and weight will be measured at every study visit.

Cannabis Use Outcome measures: Cannabis use will be recorded by the timeline followback (TLFB) method (Litten and Allen 1992) modified for cannabis and confirmed by creatinine-normalized quantitative urine THC levels. Other substance (including nicotine and alcohol) use self-report data will also be gathered during the TLFB interview. Urine samples for quantitative urine THC levels and creatinine will be collected under directly-observed conditions during screening and at each study visit (twice weekly). Creatinine levels can be used to control for urine concentration variability and screen for adulterated samples. Creatinine-corrected quantitative urine THC levels will then be used to confirm self-reported cannabis use, using a method similar to that described by Preston et al. (Preston et al. 1997) for cocaine dependence, where an obvious pattern of new use (i.e., level more than doubles in the past two days) overrides a self-report of no use.

Cannabis Withdrawal measure: We will use the 22-item version of the Marijuana Withdrawal Checklist (MWC; Budney et al. 1999) that measures subject-rated severity as the primary outcome measure of withdrawal.

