Study: # 7343 entitled EFFECT OF CLONAZEPAM ON CANNABIS WITHDRAWAL AND RELAPSE IN TREATMENT-SEEKING PATIENTS: COMBINED INPATIENT/OUTPATIENT STUDY

PI: [name].

NCT# NCT02913924

Statistical Analysis Plan (Grant): 9/19/2013

Amended 4/15/2016 (DSMP)

Grant Submission U54 DA037842: 9/19/2013

3. Data Analysis a. Outcome Measures and Covariates

i. Primary outcome measures: 1) Cannabis use: The time to sustained relapse defined as 5 days of cannabis use over a 7 day period as recorded by the Timeline Followback method and confirmed by creatinine-normalized quantitative urine THC levels, or time to dropout of study, whichever comes first (survival outcome).

ii. Secondary outcome measures: These measures are designed to capture changes in cannabis consumption patterns and other symptoms not measured by the primary outcome measures.

1) Abstinence during the final two weeks (study weeks 11 and 12) of the study (dichotomous)

2) Retention in treatment (survival outcome)

3) Days per week of cannabis use (continuous longitudinal)

4) Cannabis withdrawal: measured by weekly Marijuana Withdrawal Checklist (continuous longitudinal)5) Cannabis craving: measured by weekly Marijuana Craving Questionnaire (continuous longitudinal)

6) Sleep disturbance: measured by the Medical Outcomes Study—Sleep Scale (continuous longitudinal)

iii. Covariates: 1) Demographic characteristics (e.g., gender, age) 2) Baseline severity of cannabis use (measured by the quantity of cannabis per using day at baseline)

iv. Other measures: Adverse effects, as measured by the Systematic Assessment for Treatment and Emergent Events (SAFTEE), will be assessed, including potential effects on compliance and outcome.

b. Sample Size and Randomization: The Research Core will supervise randomization procedures. A total of 72 patients will be recruited over a 2.5-year period and randomized to the double-blind treatment trial, with 36 patients randomized to each of the two treatment groups, nabilone/XR-NTX arm and placebo arm. The randomization sequence will be balanced in blocks of random size (2, 4, 6) to prevent clinicians from guessing what the next patient's treatment might be.

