Hypothesis 2: Nabilone and XR-NTX will significantly promote abstinence from cannabis use as compared to placebo during the final 2 weeks of study (weeks 11 and 12). The following logistic regression model will be used: (2) logit(Yij = 1) = $\beta 0 + \beta 1$ Ij + $\beta 2$ Uij + ϵ ij where Yij is a dichotomous measure indicating whether the i th subject in the treatment group j has used cannabis during the final 2 weeks of study, with Yij = 1 for non-abstinent and Yij = 0 for abstinent during the final 2 weeks of study; Uij is the vector of all appropriate covariates; Ij is the indicator variable for treatment with nabilone and XR-NTX; and ϵ ij is a random error term. Significant Ij indicates that the odds of abstinence from cannabis during the final 2 weeks are different in each group.

Hypothesis 3: Nabilone and XR-NTX will significantly increase time to dropout as compared to placebo. To test the secondary hypothesis 3, we will use the same model as in (1) to test whether retention is different between the two groups.

Hypothesis 4: Over time, the days of weekly cannabis use will be significantly less in the Nabilone and XR NTX group as compared to the placebo group. This hypothesis will be tested using the following

longitudinal mixed effects model: (3) Yijt = $\beta 0 + \beta 11j + \beta 2t + \beta 3t^*1j + \beta 4Uij + sij + \epsilon ijt$ where Y ijt is the days of cannabis used over a one-week period by the i th subject in the treatment group j at week t (t =1, 2, ..., 12); Uij is the vector of covariates; Ij is the indicator variable for treatment with nabilone and XR-NTX; sij is a random intercept for subject i and ϵijt is a random error term. Significant interaction t*Ij indicates that the effect of each treatment group is different over time (that corresponds to rejecting null hypothesis that $\beta 3= 0$). If so, the effect of time will be estimated for each group separately and the groups will be compared (using contrast) in the last time point t=12. If the interaction term is not significant (i.e., the difference between the treatment arms does not change over time), we will refit the model without the interaction term and test the significance of the main effect of treatment (i.e. rejecting the null hypothesis that $\beta 1 = 0$).

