Hypothesis 5: Over time, subjects in the nabilone and XR-NTX group will experience significant reduction in the pattern of cannabis withdrawal symptoms (measured as mean Marijuana Withdrawal Checklist score per week) compared to the subjects in the placebo group.

Hypothesis 6: Over time, subjects in the nabilone and XR-NTX group will exhibit significantly reduced cannabis cravings (as measured by Marijuana Craving Questionnaire) compared to subjects in the placebo group.

Hypothesis 7: Over time, subjects in the nabilone and XR-NTX group will experience significantly less sleep disturbance (as measured by the Medical Outcomes Study Sleep scale) compared to subjects in the placebo group. To test the secondary hypotheses 5, 6, and 7 we will use the same model as in (3) where Yijt is the appropriate outcome variable (as specified for each hypothesis) for the i th subject in the treatment group j at week t (t =1, 2, ..., 12). We will first test the interaction effect of group and time as described for Hypothesis 4.

iii. Exploratory Analyses We will explore whether there are differences between the two groups with respect to the number of adverse effects, side effects, and tolerability in relation to the primary outcome. We will also explore whether co-occurring psychiatric disorders, gender, concurrent treatment exposure, trauma history, or impulsivity are predictors of treatment outcome.

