f. Power Analysis: The sample size of 72 was chosen to ensure sufficient power (at least 80%) of a twosided test with level of significance α =0.05 for detecting difference between the two experimental treatments with respect to time to relapse, based on the Cox proportional hazards model. We expect that the nabilone and XR-NTX group will have greater time to relapse than the placebo group. The rate of retention for the placebo group at 12 weeks can be expected to be 15% based on our prior studies. With 36 per arm, we will be able to detect a difference in retention (without relapse) rates between placebo versus nabilone and XR-NTX of approximately 25% (i.e. 15% on placebo vs 39.6% on nabilone and XR-NTX). This corresponds to a hazard ratio of 0.49 (Machin et al. 1997). The proposed sample size will also enable us to estimate the retention rate of the treatment group with a 95% confidence interval, ±15%, in the worst case. The computation above was performed assuming that the covariates (i.e., baseline cannabis use and age) do not have a predictive power. The 25% rate difference is consistent with a medium to large sized effect, which is what we are seeking in this early Phase II trial. This represents an effect that would be clinically meaningful and likely to make a substantial impact on the success of XR-NTX treatment in clinical practice A2. Primary and Secondary Outcome Measures Primary Outcome Measure: (1) Cannabis withdrawal (mood, sleep quality and duration, food intake) (2) Cannabis relapse defined as (1) time to any MJ use as recorded by the timeline follow back method and confirmed by urine metabolite levels, or (2) time to dropout, whichever comes first, and (3) medication compliance (% of pills taken) or time to discontinuation. Participants who relapse will continue in the trial to obtain secondary outcome measures. Secondary Outcome Measures: (1) Abuse liability (medication liking, desire to take again) (2) Cognitive task performance (3) Side effects and tolerability.

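### SAP 3.e.iii compares the number of adverse effects with no unit, denominator or on-drug window, so the result would depend on time observed and would mix medication weeks with medication-free weeks

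*SAP*

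**What the plan says.** The status of side effects varies between sections. The protocol's list of secondary outcomes and SAP A2 both include "3) Side effects and tolerability". SAP 3.a.ii does not list them among the secondary outcomes; 3.a.iv places them under other measures: "Adverse effects, as measured by the Systematic Assessment for Treatment and Emergent Events (SAFTEE), will be assessed". SAP 3.e.iii, headed as exploratory, has the only between-group comparison: "differences between the two groups with respect to the number of adverse effects, side effects, and tolerability in relation to the primary outcome".

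The protocol (Outpatient Study Assessments) says that SAFTEE, "adapted for clonazepam will be performed weekly to identify adverse symptoms", and Table 3 schedules it at baseline and in every week from 1 to 12. Table 2 ends study medication on day 56, after a taper in week 8, and leaves weeks 9-12 without study drug. Sample #1 requires 60 completers and gives the "Projected number of subjects who will be enrolled to obtain required number of completers 80".

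No rule elsewhere settles how incomplete follow-up enters the comparison:

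- SAP 3.c treats dropout as relapse in the primary analysis only. Its mixed models are for secondary outcome variables, and the section 3 list of these omits adverse effects.
- SAP C3 applies mixed models to the primary outcome variables. Its repeated-measures ANOVA list does not include adverse effects.
- The protocol's section on removal from the study keeps patients who are removed for medical reasons, or who ask to withdraw, in open treatment. It does not say whether SAFTEE continues or whether those weeks count.

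**The concern.** A number of events collected at weekly visits grows with the number of visits attended. With 60 completers from 80, one patient in four is expected to have a shortened record. If one arm is observed for longer, it accumulates more recorded effects at the same underlying rate, and a difference in retention would be read as a difference in tolerability. If patients leave because of side effects, the count can instead hide harm.

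The second problem does not need unequal dropout. A total to week 12 adds four weeks without study drug to eight weeks with it. If drug-related effects stop with the drug, this pulls a real difference toward no difference.

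The drug is a controlled substance given to patients with a substance use disorder, so the tolerability comparison should be one that a reader can interpret.

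**Working it through.** **Plan's own figures.** The plan states no safety figure. Its nearest figure is in SAP A4: 15% v 41.81% surviving, 40 per arm, hazard ratio 0.46. This reproduces: ln(0.4181)/ln(0.15) = 0.460. Freedman's formula then needs 58 events, so N = 2 × 58/(2 − 0.15 − 0.4181) = 81, against the stated 80. That endpoint is relapse or dropout, so it does not give dropout by arm.

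**Inputs from the documents.** 40 per arm (A4); 12 weekly SAFTEE records (Table 3); 8 medication and 4 medication-free weeks (Table 2); 60/80 = 75% completion overall (Sample #1).

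**Assumptions, not in the documents.** The retention split by arm (each split below averages 75%), exponential dropout unrelated to side effects, and equal true adverse-effect rates in the two arms.

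**Step 1: observed weeks.** With retention S at week 12, L = −ln(S)/12 and mean observed weeks = (1 − S)/L. At S = 0.65, L = 0.03590 and the mean is 0.35/0.03590 = 9.75. At S = 0.85, L = 0.01354 and the mean is 0.15/0.01354 = 11.08. With a constant equal rate, the count ratio equals the ratio of observed weeks.

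| Retention, placebo / clonazepam | Mean weeks | Count ratio | Two-sided error of a test on counts |
|---|---|---|---|
| 75% / 75% | 10.43 / 10.43 | 1.00 | about 5% |
| 70% / 80% | 10.09 / 10.76 | 1.07 | about 6-7% |
| 65% / 85% | 9.75 / 11.08 | 1.14 | about 11% |

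The error column is from simulated trials with 0.75 events per week, gamma between-patient variance 0.4, and a Welch t-test on per-patient counts at 5%. The SAP names no test; this one is a stand-in. At 65%/85%, with rates from 0.25 to 1 per week, the error runs from about 9% (between-patient variance 0.5) to 26% (no between-patient variation).

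**Step 2: events that cluster early.** Suppose 2 per week in weeks 1-2 and 0.25 per week afterwards, equal in both arms, with 65%/85% retention. Mean observed time within the first two weeks is (1 − exp(−2L))/L = 1.930 and 1.973 weeks.

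- Placebo count: 2 × 1.930 + 0.25 × (9.750 − 1.930) = 5.81
- Clonazepam count: 2 × 1.973 + 0.25 × (11.076 − 1.973) = 6.22
- Count ratio: 6.22/5.81 = 1.07, half the excess of the constant-rate case
- Single overall rate: 5.81/9.75 = 0.596 v 6.22/11.08 = 0.562, ratio 0.94

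One overall rate per observed week is thus biased the other way, with error of roughly 7%, about the same as for counts. Compared within period, both arms show 2 and then 0.25 per week, and the ratio is 1.

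**Step 3: medication-free weeks.** With complete follow-up, a constant background rate and no drug effect after day 56, an on-drug ratio RR appears over 12 weeks as (8 × RR + 4)/12. For RR = 1.5 this is 16/12 = 1.33; for RR = 2.0 it is 20/12 = 1.67.

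**The case against.** The strongest reply is that the SAP does not prescribe a flawed test. It says only that differences will be explored "with respect to the number of adverse effects, side effects, and tolerability", and it specifies neither a per-patient total nor a t-test. This stands: the defect is that the measure is undefined, and the error rates above belong to one literal reading.

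A reader might infer that clonazepam patients will stay longer, so that the drug is bound to look less safe. The documents do not support this. For Hypothesis 3 the SAP says "we will use the same model as in (1) to test whether retention is different between the two groups", but that hypothesis is worded for nabilone and XR-NTX, as is all of section 3.e. The clonazepam power section speaks of relapse or dropout together. Reading its 15% v 41.81% as retention would give 5.38 v 8.01 observed weeks, a ratio of 1.49. However, the protocol and SAP A2 keep relapsed patients in the trial, so that gap is not a gap in follow-up.

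It can also be argued that the mixed models in SAP 3.c already cover side effects as a secondary outcome. A weekly SAFTEE count could be fitted that way. But section 3 does not list adverse effects as secondary, and its longitudinal model is assigned only to Hypotheses 4 to 7. The plan is ambiguous here, and the gap remains.

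The dilution figures assume that drug-related events end on day 56. The protocol monitors benzodiazepine withdrawal during and after the taper, so later weeks may carry drug-related events. That limits the 1.33, but it also argues for showing the two periods separately.

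Finally, the sentence is exploratory, individual events are recorded with severity and action taken, and a DSMB reviews safety. This lowers the severity.

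**Conclusion.** The concern holds as a gap in specification. Taken literally, the comparison in 3.e.iii depends on time observed and pools weeks on and off study drug, and no other section corrects either.

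Whether this produces bias from unequal follow-up is conditional. There is none if follow-up is equal by arm. A modest gap (70%/80%) gives a count ratio of 1.07 and error near nominal; a 20-point gap gives 1.14 and about 11%. These figures rest on assumed retention splits and constant equal rates. Early clustering shrinks the bias, and intolerance-driven exit can reverse it, so the documents do not establish which arm would be disadvantaged. The dilution from 1.5 to 1.33 needs no dropout gap, but it does assume no drug effect after day 56 and complete follow-up.

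Severity is minor to moderate: one exploratory analysis of an outcome that other sections call secondary.

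**What to change.** In SAP 3.e.iii, replace the number of adverse effects with SAFTEE-recorded adverse effects per observed patient-week. Analyse the weekly records with treatment and a week (or period) term, using a negative binomial model or Poisson with robust standard errors that allow for repeated weeks within a patient. Report the medication period, including the taper, separately from the medication-free weeks 9-12. State how week 9 is classed for a patient whose taper is extended, and whether weeks in open treatment after removal count. Alongside, report by arm the proportion of patients with each main type of event and the number who discontinued for side effects.

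The cost is a few sentences of SAP text and slightly more analysis; SAFTEE is already scheduled weekly, and no visit or sample size changes. The week or period term should not be dropped: a single rate with a log(observed weeks) offset assumes a constant rate, and Step 2 of the working shows the bias if events cluster early. No version of the rate corrects for dropout caused by intolerance, which is why discontinuations must be shown beside it.

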## **Specific Aims and Hypotheses**

#### Specific Aims and Hypotheses

#### Primary Outcome Measure:

(1) Cannabis withdrawal (mood, sleep quality and duration, food intake)

(2) Cannabis relapse defined as (1) time to any MJ use as recorded by the timeline follow back method and

confirmed by urine metabolite levels, or (2) time to dropout, whichever comes first, and (3) medication compliance (% of pills taken) or time to discontinuation. Participants who relapse will continue in the trial to obtain secondary outcome measures.

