A4. Power calculation and sample size Cannabis Withdrawal. We hypothesize that clonazepam will decrease symptoms of cannabis withdrawal (e.g. ,irritability, sleep efficiency). With a sample size of 80, the test of a single contrast at the 0.050 level will have >90% power to detect a 25% decrease in these ratings under conditions of medication administration compared to placebo, assuming the same between-level correlation and SD than our earlier studies. Cannabis Relapse: The time to relapse as recorded by the Timeline Follow Back method and confirmed by creatinine-normalized quantitative urine THC levels, or time to dropout of study, whichever comes first (survival outcome). The sample size of 80 was chosen to ensure sufficient power (at least 80%) of a two-sided test with level of significance 5% for detecting difference between the two experimental treatments with respect to time to relapse, based on the Cox proportional hazards model. We expect that the clonazepam group will have greater time to sustained relapse than the placebo group. The rate of survival for the placebo group can be expected to be 15% based on our prior studies. With 40 per arm, we will be able to detect a difference in proportion of surviving in placebo versus clonazepam of approximately 27% (i.e. 15% on placebo vs 41.81% on clonazepam). This corresponds to a hazard ratio of 0.46 (Machin et al. 1997). The power computation was performed assuming that the covariates (i.e., baseline cannabis

use and age) do not have any predictive power. If they do, the power of the primary hypothesis will be higher than 80%. The 26.81% rate difference is consistent with a medium to large sized effect, which is what we are seeking in this early Phase II trial. This represents an effect that would be clinically meaningful and likely to make a substantial impact on the success of clonazepam treatment in clinical practice. The proposed sample size n=40 for clonazepam group will also enable us to estimate the relapse and retention rates of the treatment group with a 95% confidence interval, $\pm 15.5\%$, in the worst case.

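### Withdrawal and relapse are both listed as primary and each is given its own 5% test, but no success rule is stated and the withdrawal contrast is not named

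*SAP*

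**What the plan says.** The protocol (Specific Aims and Hypotheses) and SAP A2 carry the same primary list. It starts with withdrawal: the SAP has "Primary Outcome Measure: (1) Cannabis withdrawal (mood, sleep quality and duration, food intake" and the protocol has "1) Cannabis withdrawal (mood, sleep quality and duration, food intake". It continues with relapse ("Cannabis relapse defined as (1) time to any MJ use as recorded by the timeline follow back method", or dropout if earlier), and ends with medication compliance or time to discontinuation.

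SAP A4 then powers two of these separately. For withdrawal it refers to "the test of a single contrast at the 0.050 level" with more than 90% power at 80 patients. For relapse it says "The sample size of 80 was chosen to ensure sufficient power (at least 80%) of a two-sided test with level of significance 5" per cent. SAP 3.d and C3 add only per-test two-tailed 5% levels.

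Other text bears on the ranking without settling it:

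- A4 uses a singular when it says that, if covariates are predictive, "the power of the primary hypothesis will be higher than 80" per cent. This sits in the relapse paragraph. C3 speaks of primary outcome variables in the plural.
- SAP 3.a names one primary, "The time to sustained relapse defined as 5 days of cannabis use over a 7 day period" (or dropout), and makes withdrawal secondary. The surrounding text (3.b, 3.e and 3.f) is written for nabilone/XR-NTX and 72 patients.
- C3 uses a cluster analysis to limit comparisons, but only among peak subjective ratings.

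The withdrawal contrast is also open. A2 names mood, sleep and food intake, while A4 gives irritability and sleep efficiency as examples. The protocol's Outpatient Study Assessments call the Marijuana Withdrawal Checklist (MWC) and the Pittsburgh Sleep Quality Index (PSQI) the primary measures of withdrawal and sleep. Table 3 schedules both at baseline and then weekly, whereas Study Procedures places the inpatient withdrawal assessment on days 2-5.

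**The concern.** With two outcomes under one primary heading, each at its own 5%, a reader cannot tell what would make this trial positive: withdrawal alone, relapse alone, either, or both. The documents neither state nor exclude an either-one-suffices reading. Under that reading the 5% level protects each test but not the trial's primary conclusion.

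Because the withdrawal contrast is unnamed, both the outcome to emphasise and the measure that represents withdrawal could be chosen after the results are seen. Such a choice could not later be shown to be independent of the data.

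**Working it through.** **1. The plan's relapse calculation.** Inputs from A4: 40 per arm, 15% versus 41.81% surviving, two-sided 5%.

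- Hazard ratio = ln(0.4181)/ln(0.15) = 0.4597, which agrees with the stated 0.46.
- Expected events = 40 × 0.85 + 40 × 0.5819 = 57.28. Dropout counts as an event, so there is no further loss.
- Freedman power = Φ(√57.28 × (1 − 0.4597)/(1 + 0.4597) − 1.960) = Φ(7.568 × 0.3702 − 1.960) = 80.0%.
- The Schoenfeld form gives 83.7%.

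The stated 80% is reproduced at a full 5% for relapse alone.

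**2. Chance of at least one significant result when neither outcome is affected.** There are two two-sided 5% tests. The documents give no correlation between them, so it is an assumption here. Formula: 1 − P(|Z1| < 1.96 and |Z2| < 1.96), with Z1 and Z2 bivariate normal. For results favouring clonazepam only: 1 − P(Z1 < 1.96 and Z2 < 1.96).

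| Assumed correlation | Either direction | Favouring clonazepam only |
|---|---|---|
| 0 | 1 − 0.95² = 9.75% | 1 − 0.975² = 4.9% |
| 0.5 | 9.1% | 4.5% |
| Upper bound, any correlation | 2 × 5% = 10% | 2 × 2.5% = 5% |
| One test alone | 5% | 2.5% |

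**3. The third listed item.** If compliance or discontinuation were also tested at 5%, the either-direction chance would be 1 − 0.95³ = 14.3% if independent, and at most 3 × 5% = 15%.

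**4. Power under two remedies at N = 80.** Inputs: 80% power for relapse and 90% for one withdrawal measure (A4 says more than 90%). Mean test statistics are 1.960 + 0.8416 = 2.8016 and 1.960 + 1.2816 = 3.2416. Correlation runs from 0 to 0.8.

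*Fixed order, relapse first.* Relapse keeps its 80%. Both are significant with probability 0.80 × 0.90 = 72.0% at correlation 0, 75.1% at 0.5 and 77.9% at 0.8. The figure for both is the same whichever test leads.

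*Holm over two tests.* The first step is at 0.025 (critical value 2.2414).

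- Power at that step: relapse Φ(2.8016 − 2.2414) = 71.2%; withdrawal Φ(3.2416 − 2.2414) = 84.1%.
- Both effects real, independent: relapse 0.712 + (0.800 − 0.712) × 0.841 = 78.6%; withdrawal 0.841 + (0.900 − 0.841) × 0.712 = 88.3%.
- Both effects real, correlations 0.5 and 0.8: relapse 78.0% and 78.0%; withdrawal 87.1% and 85.8%.
- Other outcome unaffected: each test is left with little more than its first-step power, about 71% for relapse and 84% for withdrawal.

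**The case against.** The best defence is that withdrawal and relapse are different questions in different phases: inpatient symptoms under enforced abstinence, then outpatient relapse. Reported as two separate claims in an early Phase II trial, each would properly carry its own 5%, and no adjustment would be needed. That stands as statistics, but the plan does not say that the claims are separate.

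A second defence is that the plan already ranks relapse first, through the singular wording in A4 and the single primary in SAP 3.a. This does not hold. Withdrawal comes first in both primary lists, C3 uses the plural, A4 bases both power statements on 80 patients, and 3.a belongs to text for another treatment. The same evidence means that the documents do not oblige the sponsor to put relapse first; the ranking is the sponsor's choice.

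A third defence is the cluster analysis in C3. It reduces comparisons among peak subjective ratings and does not link withdrawal to relapse.

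A reader might infer that the trial as planned carries about a 10% chance of falsely claiming benefit. The documents do not support that. The 9.75% requires that either result be enough, which is not stated, and it includes results against clonazepam; in clonazepam's favour the figure is 4.9%. Nor does 10% cap the whole primary list, which has a third item. A high assumed correlation gives no floor either: 0.8 gives 7.8% and 0.9 gives 7.0%, and nothing in the documents supports either value.

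**Conclusion.** The gap is real. Two outcomes are listed as primary with separate 5% tests and no order, split or success rule; a third item shares the list; and the withdrawal contrast is unidentified.

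The numerical consequence is conditional. It assumes that either result counts, that clonazepam affects neither outcome, and that exactly two tests are made. The one-sided error in clonazepam's favour then roughly doubles, from 2.5% to 4.5-4.9% at correlations of 0.5 to 0. Testing withdrawal components separately would raise it further, but the documents do not fix their number and A4 speaks of one contrast, so no figure is offered.

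Confidence is high on the missing rule and the unnamed contrast. The percentages rest on the assumed correlation and on the either-result reading. The matter should be corrected, at small cost, before unblinding.

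**What to change.** Before unblinding, with N kept at 80:

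1. State the success rule in both documents. If withdrawal and relapse are to be two separate claims, say so explicitly. If they support one primary conclusion, choose one of these:
   - **(a) Fixed order**, for example relapse first at two-sided 5%, then withdrawal only if relapse is significant. Relapse power stays at about 80%. Withdrawal is not confirmatory if relapse fails, so the chance of establishing both is 72-78%. Putting withdrawal first would instead reduce confirmatory relapse power to that 72-78%.
   - **(b) Holm over the two tests**, so that either can be claimed alone. Power is about 78% for relapse and 86-88% for withdrawal if both effects are real, falling to about 71% and 84% respectively if the other outcome is unaffected. The power statement should give both cases.
2. Name one inpatient withdrawal measure and one contrast over days 2-5, and say how it relates to the outpatient MWC and PSQI that the protocol also calls primary.
3. List compliance or discontinuation as secondary, in line with the protocol's Study Procedures, which place adherence and tolerability in a secondary endpoint.
4. Use one relapse definition throughout. The primary lists take any use; A4 says "We expect that the clonazepam group will have greater time to sustained relapse than the placebo group"; and SAP 3.a uses 5 days in 7. The test must refer to one event.

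The cost is wording in two documents, one choice of withdrawal measure and, under Holm, the stated loss of power.
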